| 17 | 2.2 | Secondary objectives were to compare the efficacy of ABT 50 mg versus placebo on the evolution of prodromal symptoms to aborted lesions, healing of non-primary lesions, duration of episode, duration of symptoms, healing of the aborted primary lesions and intra oral/mucosal non primary lesions, and the incidence of and time to recurrence during 9 months following treatment. Prodromal symptoms (such as pain, tenderness, itching, tingling or discomfort) are early symptoms that herald the onset of a cold sore outbreak. | |
| 26 | 5.5 | Withdraw of informed consent by the participant; | |
| | | Study intervention kit not available; Lack of compliance as determined by the Investigator/designee. | |
| 36 | 8.1.5.1 | Participants will record face images and complete 0-10 NRS HL symptom evaluation at 09:00, 14:00 and 19:00 that day with QoL OHIP scoring at the first assessment of the day. All scoring, face images and QoL OHIP will be recorded in the Science 37 Platform. All post-dose time point assessments have an allowable window of ±60 minutes. | |
| 40 | 8.2.2 | Removal of a duplicate survey graphic. Note: Example for display only and not the licensed version. Specific wording for each question may slightly differ for participants then what is displayed in the protocol. The OHIP 14 is licensed by Mapi Research Trust. | |
| 49 | 10.1 | Sponsor's medical expert for the study Name: Title: Address: Bayer Healthcare [name] | |

Version 5.0 Page: 4 of 68

Protocol Amendment 2 (Version 3.0)

The following sections were amended from Version 2.0 to Version 3.0.

Type of Amendment: Substantial

Changes which are considered significant or substantial have been made to the following sections reflected below:

| Page Number(s) | Section Number(s) | Description, paragraph or bullet point/number | |
|-------------------|----------------------|--|--|
| 12, 20 | 1.1, 3.0 | To evaluate the Global assessment at Day 14. To evaluate the adhesion time of Sitavig, the incidence of detachment or swallowing within 6 hours of dosing, and the number of tablets replaced incidence of replacing the tablet. Other Endpoints Time to cessation of symptoms, measured in hours from initial application of assigned study intervention. Cessation of symptoms is defined as the absence of sensations of pain, tenderness tingling, itching or discomfort at the site of the cold sore as measured by NRS. Observation period to determine healing will last up to 14 days (CesSymp14). The change from baseline to post-dose in NRS. The incidence of detachment or swallowing within 6 hours of dosing and the number (percentage) of subjects with the incidence. The percentage of subjects who replace the tablet among those with detachment or swallowing within 6 hours of dosing. | |
| 14 | 1.2 | Modification of Study Scheme of Treatment Phase from 8-10 days to 8-13 days. Modification of Day 14 window from \pm 1 day to \pm 2 days. | |
| 15 | 1.3 | Modification of Schedule of Activities of Treatment Phase from 8-10 days to 8-13 days. Modification of Day 14 window from ± 1 day to + 2 days. New footnote (d): The 2-day window pertains to all Visit 3 tasks except the NRS symptom scores, face images, QoL-OHIP and Global assessment which should be collected at their respective nominal times (±60 minutes) on Day 14. Footnotes e, f and g were revised accordingly. | |

Version 5.0 Page: 5 of 68

| Page Number(s) | Section Number(s) | Description, paragraph or bullet point/number | |
|-------------------|----------------------|---|--|
| 21 | 4.1.1.3 | Additionally, participants will complete face images, symptom and QoL scores on Days 2 through 10 13 with a virtual visit no later than on Day 14 (+2 days), Visit 3 using the Science 37 Platform. | |
| 35 | 8.1.3 | Randomized participants will start a 6-month Run-in phase during which they will be eligible to start study intervention. The start date for the Run-in phase is defined as the verified date of receipt of undamaged study intervention by the study participant. | |
| 36 | 8.1.4 | Participants who start to experience prodromal symptoms before the visible appearance of any signs of HL must document the start time of symptoms in Science 37 Platform, complete a predose (immediately before dosing) 0-10 NRS cold sore symptom evaluation (pain, burning sensation, itching and swelling) and a face image. | |
| 37 | 8.1.5.5 | Header: addition of days 11, 12 and 13. | |
| 37, 38 | 8.1.5.6 | Header: modification of Day 14 window from ± 1 day to +2 days. All post-dose time point assessments have an allowable window of ±60 minutes. The 2-day window pertains to all Visit 3 tasks except the NRS symptom scores, face images, QoL-OHIP and Global assessment which should be collected at their respective nominal times (±60 minutes) on Day 14. | |
| 39 | 8.2.1 | Assessed at Screening (pre-dose), Day 1 through the participant's self-reported completion of study intervention (up to on Day 14 post dose ±1 day). | |
| 41 | 8.2.3 | A question Questions that rates the IMP as a cold sore treatment and the participant's experience at the self-reported completion of study intervention (14 days post-dose) using a 5-point Likert scale. New Question Overall, I would rate the experience (ease, comfort, convenience of use etc.) of the study medication as • 0 = poor • 1 = fair • 2 = good • 3 = very good • 4 = excellent | |

Version 5.0 Page: 6 of 68

| Page Number(s) | Section Number(s) | Description, paragraph or bullet point/number | |
|-------------------|----------------------|--|--|
| 49 | 10.1 | Sponsor's medical expert for the study Name: PPD, MD Title: Affairs Address: Bayer Healthcare [name] | |
| 51 | 10.1.4 | A copy of the ICF(s) must be provided to the participant. Participants who are rescreened are required to sign a new ICF. | |
| 54 | 10.1.10 | Study monitors will perform ongoing source data verification to confirm that data entered into the eCRF and/or Science 37 platform by authorized site personnel are accurate, complete, and verifiable from source documents; that the safety and rights of participants are being protected; and that the study is being conducted in accordance with the currently approved protocol and any other study agreements, ICH GCP, and all applicable regulatory requirements in accordance to the monitoring plan. | |

Version 5.0 Page: 7 of 68

Protocol Amendment 3 (Version 4.0)

The following sections were amended from Version 3.0 to Version 4.0. Pagination was updated in this table to align with Amendment 4.

Type of Amendment: Substantial

Changes which are considered significant or substantial have been made to the following sections reflected below:

| Page Number(s) | Section Number(s) | Description, paragraph or bullet point/number | |
|-------------------|----------------------|--|--|
| 2 | Sponsor Signatory | Sponsor's medical expert for the study Name: Title: Address: Bayer Healthcare [name] | |
| 16 | 1.2 | Modification of Study Scheme Screening/Randomization Phase Within 21–35 days of the start of the Run-in Phase Modification of Study Scheme Day 1 / Day 2 – Visit 2** Modification of footnote ** Visit 2 may occur within 36 hours of Day 1 dosing time | |
| 17 | 1.3 | Schedule of Activities (SoA) Screening/Randomization Phase Within 21 35 days of Run-in start Treatment Phase Day 1 - 2 Face images and NRS symptom scores only required if a new outbreak of herpes labialis is determined suspected by the investigator. | |
| 24 | 4.1.1.1 | Participants will be screened for eligibility up to 21 35 days prior to study according to the inclusion/exclusion criteria. | |
| 24 | 4.1.1.3 | Participants will be asked to meet with the clinic via the Science 37 Platform within 24 36 hours of the start of study intervention (Day 1) | |
| 26 | 5.1 | 3. Willing to avoid, during the treatment phase, the use of anti- inflammatory (not including low-dose (81 mg) aspirin), anti- herpetic, antibiotic and antiviral agents as well as steroids or other natural products that would interfere with the immune system response; | |

Version 5.0 Page: 8 of 68

| | 4. Female participants of childbearing potential must be using a medically acceptable form of birth control for at least 1 month prior to-during screening (3 months on oral contraceptives) |
|-------|---|
| 5.2 | 13. Known medical history of renal disease, that in the judgment of the investigator is severe |
| 5.2 | 21. Participants unwilling to avoid the use of any antivirals , oral analgesics, any lip balm or zinc oxide cream, non-steroidal anti-inflammatory drug (including aspirin and probenecid) or topical pain reliever or anesthetic (e.g., benzocaine, lidocaine) as a cold sore treatment during the stud |
| | 25. Use of intramuscular and intra-articular steroids is prohibited; oral or systemic steroids within 30 days of randomization |
| | 26. Prophylactic antiviral treatment during the Follow up Phase up the Screening Phase, Treatment Phase and in the Follow Up Phase until to the first new investigator confirmed HL outbreak; |
| | 29. Participants whose occupations make them unlikely to complete a virtual clinic visit within 24 36 hours of study intervention initiation; |
| 6.1 | During screening and injury assessment, after completion of the pre treatment baseline procedures/assessments participants who meet the entry criteria |
| 6.1 | Upon successful completion of all screening assessments, randomization and participant's receipt of study intervention, participants then enter the Run-In Phase |
| 6.8 | For this study, any dose of study intervention greater than one (1) tablet being ingested will be considered an overdose. This includes tablets that were accidently swallowed requiring the participant to apply a second (backup) buccal tablet, applying two tablets to the gum, or any other situation in which a participant ingests two tablets |
| 8.1.1 | The Screening Phase will be up to 2135 days. |
| 8.1.1 | Distribute urine pregnancy test kits (2)(if applicable); |
| 8.1.4 | Prior to the start of study intervention, all female WOCBP participants MUST perform a urine pregnancy test, |
| 8.1.6 | If the investigator determines suspects a HL outbreak has started, the participant will be instructed to record additional 0-10 NRS symptom scores and face images (at the discretion of the investigator) and document the HL outbreak in Science 37 Platform. |
| 8.3.1 | Vital signs will consist of 1 3 pulse and 3 blood pressure measurements |
| | 5.2 6.1 6.8 8.1.1 8.1.1 8.1.4 8.1.6 |

Version 5.0 Page: 9 of 68

| 45 | 8.4.5 | If a pregnancy is reported while the participant is in the treatment phase, the investigator will record pregnancy information on the appropriate form and submit it to the sponsor within 24 hours of learning of the female participant's pregnancy. | |
|----|--------|--|--|
| 51 | 10.1 | Sponsor's medical expert for the study Name: PPD PharmD Title: Address: Bayer Healthcare [name] Phone: E-mail: PPD PPD PPD PPD PPD PPD PPD PPD PPD | |
| 53 | 10.1.4 | Additionally, the investigator or designee will personally sign and date the form within the Science 37 Platform. | |
| 64 | 10.4 | 3. Postmenopausal female A postmenopausal state is defined as no menses for 12-24 months without an alternative medical cause. | |

Version 5.0 Page: 10 of 68

Protocol Amendment 4 (Version 5.0)

The following sections were amended from Version 4.0 to Version 5.0. Pagination was updated in this table to align with Amendment 4.

Type of Amendment: Substantial

Changes which are considered significant or substantial have been made to the following sections reflected below:

1.1 Synopsis

Protocol Title: A Randomized, Multi-Center, Double Blinded, Self-Initiated, Single Treatment Study Comparing Sitavig® (acyclovir) 50 mg Muco-adhesive Buccal Tablet to Placebo in the Treatment of Herpes Labialis in Immunocompetent Adults

Objectives and Endpoints:

| Objectives | Endpoints |
|--|--|
| Primary | |
| To compare duration of episode (DOE) of cold sores between Sitavig and placebo in participants experiencing a recurrence of herpes labialis (HL). | Duration of episode (DOE) will be measured in hours (using the Science 37 Platform), of a single treated HL lesion. Observation period to determine healing will last up to 14 days (DurEp14). |
| | Duration of episode (DOE) is defined as the time from the initiation of treatment (study intervention initiation) to the healing of primary lesions (loss of crust) for participants who experience a vesicular lesion. For participants whose primary lesions are not vesicular in nature, duration of episode is the time from study intervention initiation to the return to normal skin as determined by the independent blinded reader of the participant's face images using a 6-point Likert scale or to the cessation of symptoms, whichever comes last. |

Version 5.0 Page: 15 of 68

| Objectives | Endpoints |
|--|--|
| Secondary | |
| To compare the incidence of aborted lesions between participants receiving Sitavig and placebo after experiencing prodromal symptoms of a recurrence of HL. To compare the incidence of recurrence of primary HL lesions between participants | Incidence of aborted lesions, defined as treated HL lesions that do not progress to the vesicular stage. A lesion that returns to normal skin without forming a vesicle or crust will be counted as an aborted lesion. Observation period to determine healing will last up to 14 days (Abort14). |
| receiving Sitavig and placebo during a 12- month follow-up period. | Incidence of recurrence of HL lesions during the 12-month follow-up period (IncRec12). |
| To compare the time to recurrence of primary HL lesions between participants receiving Sitavig and placebo during a 12-month follow-up period. To assess safety and tolerability of the investigational products. | Recurrence is determined by assessment from the investigator and documented using numerical rating scale (NRS) symptom scores and face images using the Science 37 Platform. |
| investigational products. | Time to recurrence of HL lesions, measured in days from resolution of the cold sore treated in the Treatment phase until onset of prodromal symptoms during the follow-up period (TimeRec12). |
| | Safety and tolerability measured by the Incidence of Treatment-Emergent Adverse Events |
| | The percentage of participants who have at least one recurrence during the 12-month follow up period will be calculated. |

Version 5.0 Page: 16 of 68

Other

- To compare the duration of episode in participants who used Sitavig or placebo who initiated study intervention within 1 hour of prodromal symptoms and participants who initiated study intervention after 1 hour of prodromal symptoms.
- To compare the time to cessation of symptoms in patients experiencing a recurrence of HL in participants who used Sitavig and placebo.
- To compare the quality of life in participants who used Sitavig and placebo.
- To compare the 0-10 NRS HL symptoms by time point in participants who used Sitavig and placebo.
- To evaluate the Global assessment at Day 14.To evaluate the incidence of detachment or swallowing within 6 hours of dosing, and the incidence of replacing the tablet.

- Duration of episode (DOE) will be measured in hours (using the Science 37 Platform), of a single treated HL lesion in participants who initiation study intervention within 1 hour of onset of prodromal symptoms and participants who initiated study intervention more than 1 hour after onset of prodromal symptoms.
- Time to cessation of symptoms, measured in hours from initial application of assigned study intervention.
 Cessation of symptoms is defined as the absence of sensations of pain, tenderness tingling, itching or discomfort at the site of the cold sore as measured by NRS. Observation period to determine healing will last up to 14 days (CesSymp14).
- Quality of life score, as measured by the OHIP-14 questionnaire at 3, 7 and 14 days post-dose.
- Global assessment of study intervention at Day 14.
- The change from baseline to post-dose in NRS.
- The incidence of detachment or swallowing within 6 hours of dosing and the number (percentage) of subjects with the incidence.
- The percentage of subjects who replace the tablet among those with detachment or swallowing within 6 hours of dosing.

Overall Design: This is a randomized (1:1/acyclovir: placebo), self-initiated, placebo-controlled, double-blind, multi-center parallel study.

Brief Summary:

This is a 14-day clinical trial (Treatment Phase) to test the hypothesis that Sitavig (acyclovir) buccal tablet safely and effectively reduces duration of a herpes labialis cold sore of the lip in immunocompetent adults. Eligible participants who pass screening procedures will be randomized and moved into the Run-in Phase. Participants will be randomly assigned one of two treatment groups - Sitavig (acyclovir) 50 mg buccal tablets or a placebo buccal tablet. The randomization assignment is such that there is a 1 in 2 chance of receiving the placebo treatment. Participants will have a 6 month eligibility window in which they can self-initiate treatment should prodromal symptoms start. At the start of prodromal symptoms, participants will self-

Version 5.0

Page: 17 of 68

initiate treatment and record face images as well as symptom scores over the next 14 days. Treatment consists of a single application (of the buccal tablet) beginning on Day 1. Face images and symptom scores are captured over the 14 day Treatment Phase.

Study Duration (Treatment Phase): 14 days

Study Duration (Follow up Phase): 12 months

Investigational Medicinal Product (IMP): Sitavig (acyclovir) 50 mg buccal tablet or placebo buccal tablet

Treatment Duration: 1 day

Visit Frequency: After the start of treatment, two visits within the 14 day Treatment Phase. Additional follow up by phone will occur at 3, 6, 9 and 12 months after treatment.

Condition/Disease: Herpes labialis of the lips caused by herpes simplex virus type 1 (HSV-1) or herpes simplex virus type 2 (HSV-2).

Study Hypothesis: Sitavig (acyclovir) buccal tablet effectively reduces the duration of a cold sore of the lips.

Health Measurement/Observation: Independent blinded lesion evaluation using a 6-point Likert scale and 0-10 NRS symptom scores will occur pre and post treatment.

Intervention Groups: Participants will be randomized in 1:1 fashion (active or placebo) with a single dose of study intervention.

Data Monitoring/Other Committee: No

Version 5.0 Page: 18 of 68

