4.1.1.3 Treatment Phase

Once participants experience prodromal symptoms, they will take face images and self-initiate treatment (study intervention) preferably **within one hour** and before the visible appearance of any signs of HL lesions according to the product instructions. Participants will also be completing HL symptom scores (pain, tenderness, itching, tingling and discomfort) as well as Quality of Life (QoL) scoring using the Oral Health Impact Profile (OHIP) and during the next 10 days within the Science 37 Platform. Participants will then be under evaluation for healing of the primary lesion(s) up to 14 days.

Participants will be asked to meet with the clinic via the Science 37 Platform within 36 hours of the start of study intervention (Day 1) and complete face images, symptom and QoL scores using the Science 37 Platform. Additionally, participants will complete face images, symptom and QoL scores on Days 2 through 13 with a virtual visit on Day 14 (+2 days), Visit 3 using the Science 37 Platform.

Version 5.0 Page: 26 of 68

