8.1.4 Treatment/Evaluation Phase (Day 1)

Participants who start to experience prodromal symptoms before the visible appearance of any signs of HL must document the start time of symptoms in Science 37 Platform, complete a pre-dose (immediately before dosing) 0-10 NRS cold sore symptom evaluation (pain, burning sensation, itching and swelling) and a face image. Prior to the start of study intervention, all WOCBP participants MUST perform a urine pregnancy test, and verify that the results are negative (not pregnant), and record in the Science 37 Platform. After verification of a negative pregnancy test result, the participant may self-initiate study intervention.

Any participant who has a positive pregnancy test or is not sure of the results must contact the Science 37 study team immediately. Participants with a verified positive pregnancy test must not self-administer study intervention and will be withdrawn from the study.

Participants must always record pre-dose NRS and a face image irrespective of the start time of prodromal symptoms in the Science 37 Platform. After the completion of all pre-dose procedures, participants will be instructed to self-administer one (1) tablet. Should the buccal tablet adhere to the upper gum correctly, a second dose/tablet is NOT applied. A second tablet in the treatment kit is provided and labeled "BACKUP". The backup tablet should only be used if an issue occurs applying the first tablet (see Section 6.5).

After dosing, participants will complete the 0-10 NRS cold sore symptom evaluation, and face images at 09:00, 14:00 and 19:00 that day within Science 37 Platform. Depending on time of day study intervention is started, some Day 1 assessments and face images may not be collected if the time (minus the 60 minute window) occurs before the time of dosing. If dosing is started after 19:00, then post-dose NRS and face images will be collected starting the next day at 09:00. All post-dose time point assessments (NRS and face images) have an allowable window of ± 60 minutes.

Version 5.0

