8.2.2 Oral Health Impact Profile (OHIP)

Developed from the OHIP-49 questionnaire, the OHIP-14 is a 14-part quality of life (QoL) questionnaire about the social impact of oral disease. The OHIP-14 consists of a set of questions measuring the functional limitation, clinical pain, psychological discomfort, clinical disability, psychological disability, social disability and handicap of persons that could arise as a result of problems with the teeth or mouth. Questions are answered using a 6-point Likert scale [9].

| | Very Often | Fairly Often | Occas- ionally | Hardly ever | Never | Don't know |
|---|---------------|-----------------|-------------------|----------------|-------|---------------|
| 1. Have you had trouble pronouncing any words because of problems with your teeth or mouth? | 0 | 0 | 0 | 0 | 0 | 0 |
| Have you felt that your sense of taste has worsened because of problems with your teeth or mouth? | 0 | 0 | 0 | 0 | 0 | 0 |
| 3. Have you had painful aching in your mouth? | 0 | 0 | 0 | 0 | 0 | 0 |
| Have you found it uncomfortable to eat any foods because of problems with your teeth or mouth? | 0 | 0 | 0 | 0 | 0 | 0 |
| 5. Have you been self conscious because of your teeth or mouth? | 0 | 0 | 0 | 0 | 0 | 0 |
| Have you felt tense because of problems with your teeth or mouth? | 0 | 0 | 0 | 0 | 0 | 0 |
| 7. Has your diet been unsatisfactory because of problems with your teeth or mouth? | 0 | 0 | 0 | 0 | 0 | 0 |
| Have you had to interrupt meals because of problems with your teeth or mouth? | 0 | 0 | 0 | 0 | 0 | 0 |
| Have you found it difficult to relax because of problems with your teeth or mouth? | 0 | 0 | 0 | 0 | 0 | 0 |
| Have you been a bit embarrassed because of problems with your teeth or mouth? | 0 | 0 | 0 | 0 | 0 | 0 |
| 11. Have you been a bit irritable with other people because of problems with your teeth or mouth? | 0 | 0 | 0 | 0 | 0 | 0 |
| Have you had difficulty doing your usual jobs because of problems with your teeth or mouth? | 0 | 0 | 0 | 0 | 0 | 0 |
| 13. Have you felt that life in general was less satisfying because of problems with your teeth or mouth? | 0 | 0 | 0 | 0 | 0 | 0 |
| 14. Have you been totally unable to function because of problems with your teeth or mouth? | 0 | 0 | 0 | 0 | 0 | 0 |

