9.4.4 Other Endpoints

- Duration of episode (DOE) will be measured in hours (using the Science 37 Platform), of a single treated HL lesion in participants who initiation study intervention within 1 hour of onset of prodromal symptoms and participants who initiated study intervention more than 1 hour after onset of prodromal symptoms.
- Time to cessation of symptoms, measured in hours from the 1st dose of assigned study intervention. Cessation of symptoms is defined as the absence of sensations of pain, tingling, or burning at the site of the cold sore. Observation period to determine healing will last up to 14 days (CesSymp14).
- Quality of life score, as measured by the OHIP-14 questionnaire at 3, 7 and 14 days post-dose will be analyzed using CMH method with a modified ridit score.
- Global assessment of treatment efficacy at Day 14 using a 5-point scale (0=none, 1=poor, 2=fair, 3=good, 4=excellent) will be analyzed using CMH method with a modified ridit score.

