7.7.3 Analysis of Other Efficacy Endpoints

The analysis of other endpoints will be performed on ITT population.

- **Duration of episode (DOE)** will be measured in hours (using the Science 37 Platform), of a single treated HL lesion in subjects who initiate study intervention within 1 hour of onset of prodromal symptoms and subjects who initiated study intervention more than 1 hour after onset of prodromal symptoms. DOE will be analyzed similarly to the analysis of primary efficacy endpoint using KM method. Individual subject data Listing for DOE will be presented.
- Fine to cessation of symptoms, measured in hours from the initiation of first dose of study drug. Cessation of symptoms is defined as the absence of sensations of pain, tingling, or burning at the site of the cold sore. Observation period to determine healing will last up to 14 days. Time to cessation of symptoms will be analyzed similarly to the analysis of primary efficacy endpoint using KM method. Individual subject data listing for Time to cessation of symptoms will be presented.
- ➤ Quality of life score, as measured by the OHIP-14 questionnaire at 3-, 7- and 14-days post-dose will be analysed using Cochran-Mantel-Haenszel (CMH) method with a modified ridit score. The number and percentage of subjects will be summarized for each question/item in OHIP-14 questionnaire by scheduled visits and treatment groups. The actual values of OHIP-14 weighted score for subscale category questions will be summarized by scheduled visits and treatment groups. The post-dose values will be compared between the Sitavig and placebo groups using two sample t-test assuming the normality of data and if the data is non-normal then Wilcoxon Rank-Sum test (also known as the Mann-Whitney U test) will be used. Please refer the Section 9.2 in this SAP for weight factors associated with subscale category questions. Individual subject data listing for OHIP-14 will be presented.
- ➤ Global assessment of treatment efficacy at Day 14 using a 5-point scale (0=none, 1=poor, 2=fair, 3=good, 4=excellent) will be analysed using CMH method with a modified ridit score. The number and percentage of subjects will be summarized for Global assessment of treatment efficacy. Individual subject data listing for Global evaluation will be presented.

CONFIDENTIAL Page 24 of 31

Private and Confidential Study No 21755 Date: DEC 18, 2023

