- The change from baseline to post-dose in NRS. The actual and the change from baseline values of NRS score for each symptom/question will be summarized by scheduled visits and treatment groups. The change from baseline to post-dose values will be compared between the Sitavig and placebo groups using two sample t-test assuming the normality of data and if the data is non-normal then Wilcoxon Rank-Sum test (also known as the Mann-Whitney U test) will be used. Individual subject data Listing for NRS scores will be presented.
- The incidence of detachment or swallowing within 6 hours of dosing will be reported by treatment groups. The percentage of subjects with detachment or swallowing within 6 hours of dosing will be compared between the two treatment groups using the Chi square or Fisher's Exact test for homogeneity of proportions for categorical data. Individual subject data Listing for incidence of detachment or swallowing within 6 hours of dosing will be presented.
- ➤ The percentage of subjects who replace the tablet among those with detachment or swallowing within 6 hours of dosing will be analysed using the Chi square or Fisher's Exact test for homogeneity of proportions for categorical data. Individual subject data Listing of subjects who replace the tablet among those with detachment or swallowing within 6 hours of dosing will be presented.

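### OHIP-14 has no scheduled pre-treatment score and its post-dose comparison uses no covariate, so the plan gives up some precision on an Other endpoint

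*Protocol*

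**What the plan says.** The endpoint is "Quality of life score, as measured by the OHIP-14 questionnaire at 3, 7 and 14 days post-dose" (Protocol 1.1, repeated in Section 3). The Schedule of Activities (1.3) marks OHIP-14 on Days 3, 7 and 14 only, and the daily procedures in 8.1.5.2, 8.1.5.4 and 8.1.5.6 agree. OHIP-14 is not in the Visit 1 list (8.1.1). Before dosing, Section 8.1.4 asks for the symptom scale and a photograph: "Participants must always record pre-dose NRS and a face image irrespective of the start time of prodromal symptoms in the Science 37 Platform".

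One narrative section departs from the schedule. Protocol 4.1.1.3, repeated in SAP 2.2, has quality-of-life scoring at the visit within 36 hours of dosing and states: "Additionally, participants will complete face images, symptom and QoL scores on Days 2 through 13 with a virtual visit on Day 14 (+2 days". These times conflict with the Schedule of Activities, but all fall after dosing.

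For analysis, Protocol 9.4.4 has "Quality of life score, as measured by the OHIP-14 questionnaire at 3, 7 and 14 days post-dose will be analyzed using CMH method", with modified ridit scores. SAP 7.7.3 keeps this and adds "The actual values of OHIP-14 weighted score for subscale category questions will be summarized by scheduled visits and treatment groups" and "The post-dose values will be compared between the Sitavig and placebo groups using two sample t-test assuming the normality of data", with the Wilcoxon rank-sum test if the data are non-normal. No covariate is named. For NRS the same section works from baseline: "The change from baseline to post-dose values will be compared between the Sitavig and placebo groups using two sample t-test".

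**The concern.** The questionnaire is not specific to cold sores. Protocol 8.2.2 describes it as covering limitations up to and including "handicap of persons that could arise as a result of problems with the teeth or mouth". A person's ordinary oral complaints can therefore enter every score, and with no adjustment that between-person variation stays in the error term. The issue may be greatest on Day 14, since the protocol introduction gives a usual lesion duration of about 7 to 10 days and many lesions should have healed by then.

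At stake is the chance of detecting a real difference on a stated quality-of-life objective. Without a baseline score, OHIP-14 balance between the arms also cannot be described, and the baseline table in SAP 7.2 covers demographics and body size only.

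**Working it through.** **Is there a pre-treatment score anywhere?**

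| Place | OHIP-14 or QoL timing | Before dosing? |
|---|---|---|
| Protocol 1.1, 1.3, 3, 8.1.5; SAP 5.3 | Days 3, 7, 14 | No |
| Protocol 4.1.1.3; SAP 2.2 | Visit within 36 hours; Days 2 to 13 | No |
| Protocol 8.1.1 (Visit 1) | Not listed | – |
| Protocol 8.1.4 (Day 1, pre-dose) | Not listed; NRS and image only | – |

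No section supplies one. SAP Section 4 defines baseline in general terms, but there is no OHIP-14 value for the definition to act on.

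**What would a covariate gain?** The plan has no figure to reproduce: the sample-size text is redacted, and no OHIP-14 effect size, SD or correlation is visible. The values of r below are therefore assumptions. Relative to comparing post-dose scores alone (variance set to 1):

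- ANCOVA variance = 1 − r²; standard-error ratio = √(1 − r²)
- equivalent sample multiplier = 1/(1 − r²)
- change-score variance = 2(1 − r)

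| r | ANCOVA variance | SE ratio | Sample multiplier | Change-score variance |
|---|---|---|---|---|
| 0.1 | 0.99 | 0.995 | 1.01 | 1.8 |
| 0.2 | 0.96 | 0.980 | 1.04 | 1.6 |
| 0.3 | 0.91 | 0.954 | 1.10 | 1.4 |
| 0.5 | 0.75 | 0.866 | 1.33 | 1.0 |
| 0.6 | 0.64 | 0.800 | 1.56 | 0.8 |

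For example, at r = 0.5: 1 − 0.25 = 0.75, and 1/0.75 = 1.33.

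**In participants.** Assume a standardized difference of 0.3 (not from the documents), two-sided alpha 0.05, 80% power and 1:1 allocation. The post-only comparison needs 2 × (1.960 + 0.842)²/0.3² = 174.4, so 175 per arm. Multiplying 174.4 by 1 − r² and rounding up gives 173, 168, 159, 131 and 112 per arm for the five rows. With 175 per arm, ANCOVA power would be 80.5%, 81.7%, 83.7%, 90.0% and 93.9%.

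**Covariate or change score?** The change score beats the post-only comparison only when 2(1 − r) < 1, that is r > 0.5. It never beats ANCOVA, because 2(1 − r) − (1 − r²) = (1 − r)², which is not negative.

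**Which r is likely for a Visit 1 score?** Three features point low:

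- Visit 1 is symptom-free (study scheme) and can precede dosing by 35 days plus the six-month run-in, about seven months.
- The form in SAP 9.2 asks about the current day, so it is a snapshot and not a usual level.
- Exclusions 5 and 6 remove some oral disease, and with it some background variation.

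A symptom-free score should also predict Day 3 worst, when the outbreak drives the answers, and Day 14 best, when little treatment difference may remain. One r for all three days is a simplification.

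**The case against.** The best defence is that nothing here is wrong. In a 1:1 randomized trial an unadjusted post-dose comparison is legitimate, OHIP-14 is neither primary nor secondary, and the plan promises change from baseline only for NRS. All of that stands, and it limits the point to efficiency.

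Three stronger readings are tempting, and the documents support none of them.

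- **Bias.** A reader might infer that a chance imbalance in oral complaints would be mistaken for a drug effect. The test's error rate already allows for chance imbalance.
- **No usable covariate.** The pre-dose NRS is compulsory and is collected in the same platform. It measures cold-sore symptoms, not general oral health, so it is only a partial substitute; its correlation with OHIP-14 is also unknown.
- **A gain of a third or a half.** That requires r of 0.5 to 0.6, which the documents do not give. At r = 0.1 to 0.2 the gain is 1% to 4%.

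Two further objections hold. The r² formula belongs to linear ANCOVA and does not carry over directly to the Wilcoxon or CMH analyses. And adding a Visit 1 questionnaire means a protocol amendment with IRB/IEC approval (Protocol 10.1.1), not just one more mark in the schedule.

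**Conclusion.** The point holds as a modest, optional gain in precision. No pre-treatment OHIP-14 is scheduled, and SAP 7.7.3 adjusts for nothing, although a pre-dose symptom score will be available. The equivalent sample gain from one covariate runs from about 1% (r = 0.1) to 56% (r = 0.6). For a Visit 1 score the low end is plausible. For the pre-dose NRS the documents give no basis for placing r in that range. These figures assume linear ANCOVA and one correlation across the three days. The planned comparison remains valid and the primary conclusion is untouched.

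**What to change.** **SAP wording only, before unblinding.** In SAP 7.7.3, replace the t-test/Wilcoxon comparison of the weighted OHIP-14 scores at Days 3, 7 and 14 with ANCOVA, or rank ANCOVA if non-normal, adjusting for the Day 1 pre-dose NRS scores. The wording should settle three details:

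- How the NRS items enter, for example as their mean.
- Which items count. Protocol 8.1.4 lists pain, burning, itching and swelling, while 8.2.1 lists pain, tenderness, itching, tingling and discomfort; the two must be reconciled.
- What happens if the pre-dose score is missing. The general baseline definition in SAP Section 4 would then fall back on the symptom-free Screening score, which is a different quantity.

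Do not use a change score instead. The protocol's CMH analysis can stay; record the addition in SAP 7.13. This costs no new data.

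**Where Visit 1 is still to come.** Add one in-app OHIP-14 at Visit 1, where platform training already takes place, and enter it as a further covariate. State how participants without it are handled. The cost is a few minutes per participant, a protocol amendment and a platform change. The documents do not show how many participants are still before Visit 1. If there are none, this part falls away.

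**Reconcile the timing.** Bring the quality-of-life times in Protocol 4.1.1.3 and SAP 2.2 into line with the Schedule of Activities.
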